3.1 Responsibility for Analyses/In-house Blinding

The statistical analysis of the data obtained from this study will be the responsibility of the Clinical Biostatistics department of the Sponsor.

This study is being conducted as a randomized, open-label study, i.e., participants, investigators, and Sponsor personnel will be aware of participant treatment assignments after each participant is enrolled and treatment is assigned.

The Clinical Biostatistics department of the Sponsor will generate the randomized allocation schedule(s) for study treatment assignment. The algorithm for the randomized allocation of participants will be implemented in an IVRS by a study vendor.

3.2 Hypotheses/Estimation

Objectives of the study are stated in Section 3 of the protocol.

There are no hypotheses associated with any of the objectives.

3.3 Analysis Endpoints

Participant preference and satisfaction measure endpoints and safety endpoints that will be evaluated for within- and/or between-treatment differences are listed below.

3.3.1 Participant Preference and Satisfaction Measure Endpoints

Primary

- Participant preference assessed by response of MK-3475A SC on PPQ question 1

Secondary

- Participant responses to question 3 of the patient preference questionnaire
- Participant responses to question 1 of the TASQ SC and TASQ IV
- Participants' choice of MK-3475A SC for the study treatment Continuation Period

Exploratory

- Healthcare provider preference assessed by HCP question (HCPQ)

3.3.2 Safety Endpoints

Safety and tolerability will be assessed by clinical review of all relevant parameters including AEs, laboratory test results, and vital signs. Safety measurements are provided in Section 4.2.1.2 and Section 8 of the protocol.

3.4 Analysis Populations**3.4.1 Participant Preference and Satisfaction Measure Analysis Populations**

The FAS population will serve as the primary population for the analysis of participant preference and satisfaction measure data in this study. The FAS population consists of all randomized participants who:

- Receive all three doses of MK-3475A subcutaneous during the treatment crossover period
- Receive all three doses of Pembrolizumab intravenous during the treatment crossover period
- Answered at least question 1 of the PPQ at C6D1

The FAS population will be used for the analysis of the following primary and secondary endpoints:

- Participant preference assessed by response of MK-3475A SC on PPQ question 1
- Participant responses to question 3 of the patient preference questionnaire
- Participant responses to question 1 of the TASQ SC and TASQ IV

All randomized participants who choose to receive treatment intervention in the continuation period, will serve as the analysis population for the following secondary endpoint:

- Participants' choice of MK-3475A SC for the study treatment Continuation Period

3.4.2 Safety Analysis Populations

Safety Analyses will be conducted in the APaT population, which consists of all randomized participants who received at least one dose of study intervention. Participants will be included in the treatment group corresponding to the study intervention they actually received for the analysis of safety data using the APaT population.

Analyses of laboratory test results and vital signs will include only participants with at least one measurement obtained after at least one dose of study intervention. If the analysis will assess change from baseline, a baseline measurement is also required.

3.5 Statistical Methods

This is an estimation study. Since there are no hypotheses associated with any endpoints, there is no type I error control strategy.

3.5.1 Statistical Methods for Participant Preference and Satisfaction Measure Analyses

The primary objective of this study is to evaluate participant preference for MK-3475A SC based on the participant preference rate (PPR). PPR is defined as the proportion of participants indicating an overall preference for MK-3475A SC in question 1 of the PPQ. The point estimate of PPR will be provided, together with 95% CI using exact binomial method proposed by Clopper and Pearson [Clopper, C. J. and Pearson, E. S. 1934]. Additionally, PPR will be descriptively summarized by treatment arm as a supportive analysis.

The secondary participant preference and satisfaction measure variables will be summarized descriptively. For participant responses to question 3 of the patient preference questionnaire, number and percentage of participants selecting each reason will be provided. For participant responses to question 1 of the TASQ SC and TASQ IV questionnaire, number and percentage of participants selecting each option for the 12 questions will be provided. The proportion of participants who choose MK-3475A SC for the study treatment continuation period will be provided, together with 95% CI using exact binomial method proposed by Clopper and Pearson [Clopper, C. J. and Pearson, E. S. 1934].

Table 1 Analysis Strategy for Key participant preference and satisfaction measure Variables

Endpoint/Variable (Description, Time Point)	Primary vs Supportive Approach ^a	Statistical Method	Analysis Population	Missing Data Approach
Primary Endpoint Analysis				
Proportion of participants who prefer MK-3475A SC with treatment preference assessed by PPQ question 1	P	Estimation: point estimate, 95% CI using exact binomial method proposed by Clopper and Pearson	FAS	Not Applicable

Endpoint/Variable (Description, Time Point)	Primary vs Supportive Approach ^a	Statistical Method	Analysis Population	Missing Data Approach
Key Secondary Endpoints Analysis				
Participant responses to question 3 of the patient preference questionnaire	P	Frequency (%)	FAS	Participants with missing data are considered to have no response
Participant responses to question 1 of the TASQ SC and TASQ IV	P	Frequency (%)	FAS	Participants with missing data are considered to have no response
Proportion of participants who choose MK-3475A SC for the study treatment Continuation Period	P	Point estimate, 95% CI using exact binomial method proposed by Clopper and Pearson	Participants who choose to receive a treatment in continuation period	Not Applicable
FAS=Full Analysis Set. ^a P=Primary approach				

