3 HYPOTHESES, OBJECTIVES, AND ENDPOINTS

In participants at least 18 years of age with early-stage or advanced/ metastatic solid tumors.

Primary Objective	Primary Endpoint
To evaluate participant preference for MK-3475A SC	Participant preference assessed by response of MK-3475A SC on PPQ question 1
Secondary Objectives	Secondary Endpoints
To evaluate the reasons for preference for MK-3475A SC	Participant responses to PPQ question 3
To evaluate participant satisfaction with route of administration of MK-3475A SC and pembrolizumab IV	Participant responses to the TASQ SC and TASQ IV
To evaluate participants choice of administration for the study Treatment Continuation Period	Participant choice of MK-3475A SC for the study Treatment Continuation Period
To evaluate the safety and tolerability of MK-3475A SC and pembrolizumab IV	AE Discontinuation of study intervention due to AEs
Tertiary/Exploratory Objectives	Tertiary/Exploratory Endpoints
To evaluate healthcare provider preference for route of treatment administration	Healthcare provider preference assessed by HCP questionnaire (HCPQ)

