4.2.1 Description of Endpoints

4.2.1.1 Patient Preference Measures

4.2.1.1.1 PPQ

The PPQ (developed and owned by Roche Products Limited [Copyright © 2013]) is an instrument that has been developed from patient interviews and includes questions to evaluate directly from participants their preference regarding mode of administration, as well as the strength of the preference, and the reason for the preference. The PPQ has been established as a questionnaire to collect data to derive the primary endpoint to assess patient preference of mode of administration, SC or IV, in several randomized crossover clinical studies [O'Shaughnessy, J., et al 2021] [Rummel, M., et al 2017]. The questions are worded as described below:

Question 1 is “All things considered which method of administration do you prefer” with response options of IV, SC or no preference. This is data to support the primary endpoint of this study, proportions of patients who prefer IV, SC or have no preference.

Question 2 is “If you have a preference for one of the administration routes, how strong is the preference?” with response options of very strong, fairly strong, not very strong.

Question 3 asks patients “If you have a preference for one of the administration routes, what are the TWO main reasons for your preference?” with response options of feels less emotional distressing, requires less time in the clinic, lower level of injection-site pain, feels more comfortable during administration, and option for “other, please specify _____”

allowing the respondent to specify the reason. The participant responses to this question supports the secondary endpoint of proportions of the reasons for patient preference.

As this questionnaire is the primary and secondary endpoint of this study, completion of the questionnaire must be checked BEFORE the participant leaves the site at Cycle 6.

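### PPQ question 3 is tabulated over the whole FAS without regard to question 1, so the percentages mix reasons for preferring IV with reasons for preferring SC

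*SAP*

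**What the plan says.** Protocol section 3 gives the secondary objective as "To evaluate the reasons for preference for MK-3475A SC", with the responses to PPQ question 3 as its endpoint.

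Protocol 4.2.1.1.1 describes the two items involved. Question 1 asks for the preferred method, "with response options of IV, SC or no preference". Question 3 reads "If you have a preference for one of the administration routes, what are the TWO main reasons for your preference". Its listed reasons (less distress, less clinic time, less injection-site pain, more comfort, or a free-text reason) do not name a route. The same section says of question 3: "The participant responses to this question supports the secondary endpoint of proportions of the reasons for patient preference".

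SAP 3.5.1 gives the analysis: "For participant responses to question 3 of the patient preference questionnaire, number and percentage of participants selecting each reason will be provided". On the population, SAP 3.4.1 says "The FAS population will be used for the analysis of the following primary and secondary endpoints", and question 3 is in the list that follows. Besides the six crossover doses, FAS membership requires only that the participant "Answered at least question 1 of the PPQ at C6D1". SAP Table 1 repeats the FAS for question 3, gives a frequency and percentage as the method, and sets the missing-data rule: "Participants with missing data are considered to have no response". Protocol Table 7 asks only for a descriptive summary in the FAS.

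The only further split in SAP 3.5.1 is the preference rate by treatment arm. That is the order in which the routes were given, not the route preferred.

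**The concern.** A question 3 answer is a reason for preferring SC only if the same participant answered SC on question 1. The plan never applies that condition. Three things follow from the text as it stands.

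- **Numerator.** A reason ticked by someone who prefers IV counts the same as one ticked by someone who prefers SC. Injection-site pain and comfort during administration are plausible reasons for either route, and protocol 2.3 itself expects injection reactions with MK-3475A. The table cannot show which route a reason supports.
- **Denominator.** Participants who prefer IV or have no preference stay in it, which dilutes the reasons that belong to SC.
- **Blank answers.** A participant with no preference has nothing to report on question 3. No rule says whether that blank is missing or not applicable.

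At stake is how one named secondary objective is read. The published percentages could be taken as reasons for choosing SC when they describe a mixture.

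**Working it through.** **Inputs.** SAP 3.8 gives 144 randomized, about 20% dropout, about 115 evaluable, and Table 3 scenarios of 63, 69, 75 and 80 participants preferring SC. Protocol 2.2.1 cites SC preference of 85% and 91.5% in two earlier studies of other SC products. The documents give no rates for how often each reason is chosen, so the rates used below are assumptions.

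**The plan's own figures.** Average dropout is (14% + 13% + 33%)/3 = 20%, and 144 × 0.80 = 115.2. The Clopper-Pearson limits in SAP Table 3 reproduce: 63/115 = 54.8% (45.2, 64.1); 69/115 = 60.0% (50.4, 69.0); 75/115 = 65.2% (55.8, 73.9); 80/115 = 69.6% (60.3, 77.8). There is no arithmetic error in the plan.

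**Who is in the question 3 denominator.** Those not preferring SC number 115 − n(SC). For the cited rates, 0.85 × 115 = 97.75, taken as 98, and 0.915 × 115 = 105.2, taken as 105.

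**Effect on a reported percentage.** As planned, percentage = (SC-preferrers choosing the reason + IV-preferrers choosing it)/115. For the objective, percentage = SC-preferrers choosing it/n(SC).

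- Reason A (assumed): chosen by 80% of SC-preferrers and nobody else. Planned value = 0.8 × n(SC)/115; value for the objective = 80%.
- Reason B (assumed): chosen by 30% of SC-preferrers and 70% of IV-preferrers. Value for the objective = 30%. The planned value depends on how the remainder divides. If all prefer IV it is (0.3 × n(SC) + 0.7 × [115 − n(SC)])/115. If all have no preference it is 0.3 × n(SC)/115.

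| Prefer SC | Do not prefer SC | Share of 115 | Reason A as planned | Reason B as planned, rest all no preference | Reason B as planned, rest all IV |
|---|---|---|---|---|---|
| 63 | 52 | 45.2% | 43.8% | 16.4% | 48.1% |
| 80 | 35 | 30.4% | 55.7% | 20.9% | 42.2% |
| 98 (85% cited) | 17 | 14.8% | 68.2% | 25.6% | 35.9% |
| 105 (91.5% cited) | 10 | 8.7% | 73.0% | 27.4% | 33.5% |

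For example, with 63 preferring SC: A = 50.4/115 = 43.8%; B = 18.9/115 = 16.4%, or (18.9 + 36.4)/115 = 48.1%.

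One result needs no assumed rate. A reason given only by SC-preferrers can never show above the SC preference rate itself, which is 55-70% in the Table 3 scenarios, even if every one of them gives it.

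**The case against.** **Pooling is inferred.** The SAP never says that all reasons go in one column. An analysis set says who is eligible and does not forbid display by question 1 answer, so a programmer might add the split unprompted. It is true that pooling is an inference. But a single frequency on the FAS, with no condition on question 1, is what the text specifies.

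**The protocol words the endpoint generally.** Protocol 4.2.1.1.1 speaks of reasons for patient preference, without naming a route, and the SAP table fits that wording. This stands: the mismatch begins within the protocol, between the SC-specific objective and the wider endpoint description, and is not the SAP's alone. The objective in protocol section 3 is still about SC, and no other planned analysis serves it.

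**No-preference participants.** A reader might infer that they are coded as non-responders. The documents do not establish this. The rule covers missing data, and because question 3 is conditional on having a preference, a blank can equally be read as not applicable. The defect is that the plan does not say which.

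**Size.** SAP Table 3 illustrates interval width and is not a forecast. The protocol's cited evidence points to higher SC preference, where the distortion is modest. This also stands, and both ranges belong in any statement of size.

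**Conclusion.** The point holds as a mismatch between a stated population and the objective it serves. As written, question 3 percentages describe reasons for either preference over a denominator that includes people who did not prefer SC. That group is 30-45% of the denominator in the SAP Table 3 scenarios and about 9-15% at the rates cited in the protocol. Under the assumed reason A, a true 80% would show as 44-56% or about 68-73% respectively. For a reason more typical of IV-preferrers, the direction of the error depends on how many of the rest prefer IV and how many have no preference.

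A reader might go further and conclude that the objective cannot be answered, or that the plan must not proceed without the change. The documents do not support that. Questions 1 and 3 come from the same participant in the same questionnaire, so the right table can be produced from the planned data. The endpoint is descriptive in an estimation study with no hypotheses, and the primary preference rate, its interval, the sample size and safety are unaffected. It should be fixed, but it is not critical.

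**What to change.** Amend SAP 3.4.1, 3.5.1 and Table 1 before database lock:

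- Report question 3 by question 1 answer. For this objective, use as denominator the FAS participants who answered SC on question 1.
- Show IV-preferrers in a separate, supportive column.
- State that question 3 is not applicable for participants who answered no preference.
- Show missing question 3 among SC-preferrers as its own row.

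Protocol Table 7 can stay as it is: SC-preferrers are a subset of the FAS, and the table asks only for a descriptive summary. The cost is a few lines of SAP text and one additional table column. No new data are needed, since question 1 is known for every FAS member. Both documents already allow analysis changes before final database lock through a SAP amendment.

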3.5.2 Statistical Methods for Safety Analyses

Safety and tolerability will be assessed by clinical review of AEs and other relevant parameters, including laboratory test results and vital signs. Adverse events will be summarized by MedDRA term, appropriate MedDRA levels (system organ class [SOC] and preferred term [PT]), and when specified by NCI CTCAE grade. For each participant, if multiple incidences of the same adverse events occur, the maximum severity reported will be used in the summaries.

3.5.2.1 Overall Safety Assessment

The overall safety evaluation will include a summary by treatment intervention for cycles 1-3 and cycles 4-6 in the Crossover Period, and by treatment arm in the overall study. An adverse event will be attributed to the treatment received on or before the AE start date. Adverse events that started during the first three cycles of the Crossover Period and continued into subsequent three cycles (even if the AE changed severity grade) will be summarized by the route of administration during which it first occurred. These AEs will be flagged in listings.

The overall safety endpoints include the number and percentage of participants with at least one AE, drug-related AE, serious AE, serious, drug-related AE, Grade 3-5 AE, AEOSI, who discontinue from study intervention due to an AE, or with an AE resulting in death. The number and percentage for injection-site reactions will be provided for participants who receive MK-3475A SC treatment. Point estimates and 95% CIs for the differences between treatment groups (i.e., treatment interventions for cycles 1-3 in the Crossover Period,

treatment interventions for cycles 4-6 in the Crossover Period and treatment arms in the overall study) in the percentages of participants with the event will be provided based on the criteria described below for specific AEs.

The number and percentage of participants with specific AEs will also be provided. Point estimate and 95% CIs for the difference between treatment groups in the percentage of participants with specific AEs will be provided if at least 10% of participants in any treatment group exhibit the event. The threshold of at least 10% of participants was chosen because the population enrolled in this study is in critical condition and usually experiences various AEs of similar types regardless of treatment; events reported less frequently than 10% of participants would obscure the assessment of the overall safety profile and add little to the interpretation of potentially meaningful treatment differences. In addition, difference in the percentage of participants with specific Grade 3 to 5 AEs ($\geq 5\%$ of participants in 1 of the treatment groups) and SAEs ($\geq 5\%$ of participants in 1 of the treatment groups) will also be summarized by point estimate and 95% CIs.

CIs for between treatment group differences will be provided using the Miettinen and Nurminen (M&N) method [Miettinen, O. and Nurminen, M. 1985]. CIs that are not adjusted for multiplicity should only be regarded as helpful descriptive measures for the review of the safety profile and not as a formal method for assessing statistical significance of between-group differences.

The number and percentage of participants with laboratory toxicity grade increased from baseline will be summarized by the post-baseline maximum toxicity grade per CTCAE V5.0 for each gradable laboratory test.

For continuous safety measures, such as change from baseline in laboratory, vital signs, summary statistics for baseline, on-treatment, and change from baseline values will be provided by treatment arm.

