1.3 Schedule of Activities

Details of each procedure outlined in the SoA are provided in Section 8. Unless otherwise indicated, procedures should be performed before study intervention administration. Refer to Appendix 7 for country-specific requirements.

Table 1 Study Schedule of Activities

Study Period:	Screening Phase	Intervention Phase (21-Day Cycles)							EOT/Discontinuation	Follow-up		Notes
Cycle	Screening (Visit 1)	1	2	3	4	5	6	7 to 35*	At treatment discontinuation	30 days post last dose	90 days post last dose contact	*Cycles 18-35 for NSCLC participants only.
Cycle Day	-28 to -1	1	1	1	1	1	1	1				
Schedule Window		+3	±3	±3	±3	±3	±3	±3				
Administrative Procedures												
Informed Consent	X											
Inclusion/Exclusion Criteria	X											
Participant Identification Card	X	X										The Participant Identification Card should be updated with the randomization number at the time of randomization.
Demographics and Medical History	X											
Tobacco Use Assessment (NSCLC participants only)	X											See Section 8.1.4.1 for definitions of cigarette use.
Prior/Concomitant Medication Review	
 
←
 

 
→
 
											Prior medications: Record medications taken within 28 days before first dose and medications regularly administered at intervals greater than 28 days before first dose. Concomitant medications: Record new medications started during the study through the postintervention follow-up, as well as any changes to dose, frequency, and route that occur.
Intervention Randomization		X										Randomization can occur up to 3 days before C1D1 (start of study intervention).

Study Period:	Screening Phase	Intervention Phase (21-Day Cycles)							EOT/Discontinuation	Follow-up		Notes
Cycle	Screening (Visit 1)	1	2	3	4	5	6	7 to 35*	At treatment discontinuation	30 days post last dose	90 days post last dose contact	*Cycles 18-35 for NSCLC participants only.
Cycle Day	-28 to -1	1	1	1	1	1	1	1				
Schedule Window		+3	±3	±3	±3	±3	±3	±3				
Vital Status		←-----→										Participants may be contacted for vital status at any time during the study. Collect Vital Status at 90 days post last dose in case of SAE.
Study Intervention Administration												
MK-3475A SC OR Pembrolizumab IV Administration ^a		X	X	X	X	X	X	X*				*17 cycles for adjuvant RCC and melanoma; 35 cycles for metastatic NSCLC.
Imaging Assessments												
Tumor Scan	X	←-----→										Perform per SoC for each tumor type.

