Brain Scan	X	←-----→										
Bone Scan	X	←-----→										
Safety Assessments												
Full Physical Examination Including Weight and Height	X								X			Collect height at Screening only.
Directed Physical Examination		X	X	X	X	X	X	X		X		For melanoma participants: The investigator or qualified designee should conduct a visual inspection of local recurrence and palpation of regional lymph nodes to assess regional recurrence.
Vital Signs	X	X	X	X	X	X	X	X	X	X		Temperature, HR, RR, BP, and weight.
Pregnancy Testing	X	X	X	X	X	X	X	X	X	X		POCBP require a negative pregnancy test before the start of study intervention (within 24 hours for urine or within 72 hours for serum).

Study Period:	Screening Phase	Intervention Phase (21-Day Cycles)							EOT/Discontinuation	Follow-up		Notes
Cycle	Screening (Visit 1)	1	2	3	4	5	6	7 to 35*	At treatment discontinuation	30 days post last dose	90 days post last dose contact	*Cycles 18-35 for NSCLC participants only.
Cycle Day	-28 to -1	1	1	1	1	1	1	1				
Schedule Window		+3	±3	±3	±3	±3	±3	±3				
12-lead ECG	X											Perform at Screening and as clinically indicated thereafter.
ECOG Performance Status	X	X	X	X	X	X	X	X	X	X		Evaluate within 3 days before the planned start of study intervention.
Hematology and Chemistry	X	X	X	X	X	X	X	X	X	X		Collect screening samples within 10 days before the start of study intervention. Collect on-treatment samples and review results within 72 hours before Day 1 of each cycle.
Urinalysis	X											Collect screening samples within 10 days before the start of study intervention.
HBV, HCV, HIV Testing	X											Only perform if required by the local health authority or if known history of infection.
Thyroid Function Tests (TSH, T3, T4)	X		X		X		X	X		X		Screening samples to be collected within 10 days before the first dose of study intervention. Perform at Day 1 of every other cycle starting from C2 until C35 (collect sample within 72 hours prior). Participants may be dosed in subsequent cycles after C1 while thyroid function tests are pending. Free T3 and T4 are acceptable.
PT or INR and aPTT/PTT (baseline only)	X											Collect screening samples within 10 days before the start of study intervention.

Study Period:	Screening Phase	Intervention Phase (21-Day Cycles)							EOT/Discontinuation	Follow-up		Notes
Cycle	Screening (Visit 1)	1	2	3	4	5	6	7 to 35*	At treatment discontinuation	30 days post last dose	90 days post last dose contact	*Cycles 18-35 for NSCLC participants only.

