8.1.8.1 Timing of Dose Administration

Study interventions should be administered after all procedures and assessments have been completed.

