8.4.1.2 Directed Physical Examination

For cycles that do not require a full physical examination as defined in Section 1.3, the investigator or qualified designee will perform a directed physical examination as clinically indicated prior to study intervention administration. New clinically significant abnormal findings should be recorded as AEs.

Investigators should pay special attention to clinical signs related to previous serious illnesses.

For melanoma participants: The investigator or qualified designee should conduct a visual inspection of local recurrence and palpation of regional lymph nodes to assess regional recurrence.

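### The same-day AE attribution rule can count a pre-dose Cycle 4 Day 1 finding under a route the participant has not yet received

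*SAP*

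**What the plan says.** SAP 3.5.2.1 calls for a "summary by treatment intervention for cycles 1-3 and cycles 4-6 in the Crossover Period", plus a summary by arm over the whole study. Between-group differences are planned within each of the two periods. Attribution to a route is by calendar date and includes the day itself: "An adverse event will be attributed to the treatment received on or before the AE start date". The next sentence deals with carry-over, but only for "Adverse events that started during the first three cycles of the Crossover Period and continued into subsequent three cycles"; those stay with the route under which they first occurred. Neither document mentions AE onset time, a comparison with dose time, or a rule for the day of the switch.

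The protocol puts the dose last on a treatment day. The Schedule of Activities states: "Unless otherwise indicated, procedures should be performed before study intervention administration". Section 8.1.8.1 repeats it: "Study interventions should be administered after all procedures and assessments have been completed". Section 8.4.1.2 has the investigator "perform a directed physical examination as clinically indicated prior to study intervention administration", and adds: "New clinically significant abnormal findings should be recorded as AEs". Sections 8.4.2 and 8.4.6.1 place vital signs and ECOG status before each dose. Hematology and chemistry samples are taken within 72 hours before Day 1. For thyroid tests the schedule says: "Perform at Day 1 of every other cycle starting from C2 until C35 (collect sample within 72 hours prior".

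**The concern.** C4D1 is the date of the first dose of the second route, but the scheduled examination and vital signs that day come before that dose. Something found there and dated that day can reflect only the three first-route doses. If it is filed under the second route, the onset itself is on the wrong route, which is a different matter from an AE that begins in cycles 1-3 and worsens later.

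The error crosses the arms. In Arm A an SC finding becomes an IV finding; in Arm B an IV finding becomes an SC finding. If the routes differ in AE risk, the cycles 4-6 contrast is pulled toward zero, and cycles 1-3 loses findings from its last scheduled assessment. Safety and tolerability of the two routes is a stated secondary objective, and the two crossover periods are where the SAP compares them directly.

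**Working it through.** **Reading the rule at C4D1.**
1. By the end of C4D1 the participant has received both routes, so both satisfy the rule. It gives a single answer only if it means the latest treatment by date, which is the second route.
2. The carry-over sentence does not change this. By date, an AE starting on C4D1 starts in cycle 4.
3. The protocol's post-dose exceptions (PPQ, TASQ, choice and healthcare professional questionnaires) fall at C3 or C6, so none applies at C4.

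**Effect per participant.** The SAP's evaluable number reproduces: 144 × (1 − (0.14 + 0.13 + 0.33)/3) = 144 × 0.80 = 115.2, stated as about 115. I assume 58 to 72 per arm (115/2 rounded up, to 144/2).
- One participant whose only event of a type is moved: 1/72 = 1.4 to 1.7 (1/58) percentage points, up in cycles 4-6 and down in cycles 1-3.
- Three such participants: 3/72 = 4.2 to 5.2 (3/58) points.
- The 10% threshold for a between-group interval is 6 to 8 participants (5.8 and 7.2, rounded up); the 5% threshold is 3 to 4 (2.9 and 3.6, rounded up). A few moved events can change which AEs receive an interval.

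**Dilution model (assumptions, not document figures).** Let hS and hI be constant weekly rates under SC and IV. Each AE is dated at the test that finds it. A share p of samples is taken on Day 1 itself and the rest 1 to 3 days earlier. The same reading of the rule applies at C7D1.

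*Tests at every cycle.* First-route exposure is read at C2, C3 and C4, three weeks each.
- Cycles 1-3: (9 − 3p)(hS − hI), so the share of the true difference kept is 1 − p/3.
- Cycles 4-6: Arm B has [6 + 3(1 − p)]hS + 3p·hI, and Arm A is the mirror image. The difference is (9 − 6p)(hS − hI), so the share kept is 1 − 2p/3.

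| p | Cycles 1-3 | Cycles 4-6 |
|---|---|---|
| 0 | 100% | 100% |
| 0.5 | 83% | 67% |
| 1 (worst case) | 67% | 33% |

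*Thyroid tests (C2, C4, C6).* The C2 test reads three weeks of the first route, the C4 test the other six, and the C6 test six weeks of the second route. At p = 1, cycles 1-3 keep 3/9 = 33%. In cycles 4-6, Arm A holds 6hS + 6hI and Arm B holds 6hI + 6hS, so the expected difference is zero. At p = 0 the rule moves nothing.

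**The case against.** The strongest reply is that the sentence is ambiguous rather than wrong. It does not say most recent, and the carry-over sentence shows an intent to credit the route under which an AE first occurred. That stands as evidence of intent, but the written rule does not deliver that result for an AE dated C4D1.

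Second, the rule uses the start date, not the detection date, and neither document tells sites to date onset at the visit. AEs with an earlier recorded onset are handled correctly. So are laboratory findings dated by a sample drawn before Day 1, which the 72-hour window allows. Abnormal results become AEs only if judged clinically significant (Protocol 10.3.2). All of this stands and limits the size.

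Third, a reader might infer from the model that the thyroid comparison is lost, or that two thirds of the cycles 4-6 difference disappears. The documents do not support that. They give no value for p, and both figures need p = 1. The constant-hazard model also fits immune-related events poorly: Protocol 6.6.1 says they can appear months after a dose, there is no washout, and Section 4.3.1 expects comparable exposure from the two routes.

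Fourth, same-day inclusion correctly captures infusion and injection reactions, which usually develop during or shortly after dosing. A reader might infer that every C4D1 AE should default to the first route. That would misfile acute post-dose events, because no onset time is shown to be collected.

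Finally, SAP 3.5.2.1 treats these intervals as descriptive only, and AEs of special interest get counts without between-group intervals (3.5.2.2).

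**Conclusion.** The point holds in limited form. Under the only reading of SAP 3.5.2.1 that yields a single answer, an AE found at the pre-dose C4D1 assessments and dated that day is counted under the second route and in cycles 4-6, although only the first route had been received. This can dilute the cycles 4-6 SC-versus-IV difference if the routes differ.

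The size cannot be fixed from the documents. It runs from nil, if samples and onsets are dated before C4D1, to the p = 1 worst cases above. The per-participant shift of 1.4 to 1.7 points rests on the assumed 58 to 72 per arm. The primary endpoint, the overall-study AE tables and the by-arm laboratory and vital-sign change summaries are not touched. This is a rule worth correcting before the tables are programmed; it is not a reason to doubt the safety evaluation as a whole.

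**What to change.** In SAP 3.5.2.1:
- State that an AE is attributed to the most recent route administered before its onset.
- Add a before/after-dose flag to the AE form for AEs dated on C4D1 and C7D1.
- Attribute to the first route, and to cycles 1-3, any C4D1 AE flagged as pre-dose or based on a sample or examination taken before the C4 dose. Date sample-based AEs by the sample, not the result, since dosing may go ahead while thyroid results are pending. At C7D1 the same logic keeps pre-dose AEs with the route given in cycles 4-6.
- Leave infusion/injection reactions, post-dose AEs and same-day AEs of unknown timing under the current same-day rule. Add a sensitivity summary that assigns the unknowns at C4D1 to the first route.

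The cost is one extra AE-form item and a small amount of programming, including a link between laboratory-based AEs and their samples, which the documents do not describe. No visits or samples are added.
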